5.2 Exclusion criteria

Patients meeting any of the following criteria are not eligible for inclusion in this study. No additional exclusions may be applied by the investigator in order to ensure that the study population will be representative of all eligible patients:

- 1. Patients with an active chronic disease (or stable but treated with immune therapy) of the immune system other than MS (e.g., rheumatoid arthritis, scleroderma, Sjogren's syndrome, Crohn's disease, ulcerative colitis, etc.) or with a known immunodeficiency syndrome (AIDS, hereditary immune deficiency, drug-induced immune deficiency).
- 2. Pregnant or nursing (lactating) women, where pregnancy is defined as the state of a female after conception and until the termination of gestation, confirmed by a positive hCG laboratory test.
- 3. Women of child-bearing potential, defined as all women physiologically capable of becoming pregnant, **unless** they are using highly effective methods of contraception while taking study treatment and for 30 days (30 days = 5 times the terminal half-life of siponimod) after stopping study treatment. Highly effective contraception methods include:
 - Total abstinence (when this is in line with the preferred and usual lifestyle of the patient. Periodic abstinence (e.g., calendar, ovulation, symptothermal, post-ovulation methods) and withdrawal are **not** acceptable methods of contraception
 - Female sterilization (have had surgical bilateral oophorectomy with or without hysterectomy), total hysterectomy, or tubal ligation at least six weeks before taking study treatment. In case of oophorectomy alone, only when the reproductive status of the woman has been confirmed by follow up hormone level assessment
 - Male sterilization (at least 6 months prior to screening). For female patients on the study, the vasectomized male partner should be the sole partner for that patient
 - Use of oral, (estrogen and progesterone), injected or implanted hormonal methods of contraception or placement of an intrauterine device (IUD) or intrauterine system (IUS), or other forms of hormonal contraception that have comparable efficacy (failure rate <1%), for example hormone vaginal ring or transdermal hormone contraception.
 - In case of use of oral contraception women should have been stable on the same pill for a minimum of 3 months before taking study treatment.

- Women are considered post-menopausal and not of child bearing potential if they have had 12 months of natural (spontaneous) amenorrhea with an appropriate clinical profile (e.g. age appropriate history of vasomotor symptoms) or have had surgical bilateral oophorectomy (with or without hysterectomy), total hysterectomy or tubal ligation at least six weeks ago. In the case of oophorectomy alone, only when the reproductive status of the woman has been confirmed by follow up hormone level assessment is she considered not of child bearing potential.
- 4. Sexually active males unwilling to use a condom during intercourse while taking study treatment and for 30 days (30= 5 times the terminal half-life of siponimod) after stopping study treatment. A condom is required for all sexually active male participants to prevent them from fathering a child AND to prevent delivery of study treatment via seminal fluid to their partner. In addition, male participants must not donate sperm for the time period specified above.
 - If local regulations deviate from the contraception methods listed above to prevent pregnancy, local regulations apply and will be described in the ICF.
- 5. History of malignancy of any organ system (other than localized basal cell carcinoma of the skin), treated or untreated, within the past 5 years, regardless of whether there is evidence of local recurrence or metastases.
- 6. Diabetes mellitus, unless well controlled and without known organ complications including but not limited to heart disease reduced renal function, significant retinal pathology or neuropathy.
- 7. Diagnosis of macular edema 1 year prior to screening.
- 8. Patients with active systemic bacterial, viral, or fungal infections or known to have AIDS or have positive HIV antibody.
- 9. Positive results of screening period testing for serological markers for hepatitis A, B, C and E, indicating acute or chronic infection:
 - anti-HAV IgM
 - HBs Ag and/or anti-HBc IgM
 - anti-HEV IgM (if positive IgG and/or IgM, perform HEV-RNA PCR and if negative, patient can be included).

Note: If the treating physician suspects false positive hepatitis serology results, such as an antibody pattern indicating acute hepatitis infection but no corresponding elevated liver enzymes and no signs or symptoms of liver disease, a HEV-RNA PCR will be performed and will be the deciding factor to determine whether the patient has hepatitis A, B, C, or E. If negative, the treating physician may document (in source data and in a eCRF comment) that the serology results are considered false positive and consider including the patient.

- 10. Negative for varicella-zoster virus IgG antibodies at Screening unless there is other evidence of immunity to VZV based on the CDC criteria (https://www.cdc.gov/chickenpox/hcp/immunity.html; see Appendix 1)
- 11. Have received any live or live-attenuated vaccines (including for varicella-zoster virus or measles) within 2 months of screening.
- 12. Have been treated with any of the medications listed below:

- Intravenous immunoglobulin within 2 months prior to screening
- Immunosuppressive/chemotherapeutic medications (e.g., azathioprine, methotrexate) within 6 months prior to screening
- Cyclophosphamide within 2 years prior to screening
- More than 24 months prior treatment exposure to natalizumab
- Rituximab, ofatumumab, ublituximab or cladribine within 2 years prior to randomization
- Alemtuzumab at any time
- Any mitoxantrone during previous 2 years prior to randomization or evidence of cardiotoxicity following mitoxantrone or a cumulative life-time dose of more than 60 mg/m2
- If patients treated with teriflunomide cannot or will not undergo the accelerated elimination process Appendix 6.
- Stem cell transplantation
- Lymphoid irradiation, bone marrow transplantation or other immunosuppressive treatments with effects potentially lasting over 6 months, at any time.
- 13. Patients with any medically unstable condition as determine by the investigator.
- 14. Any of the following conditions or treatments that may affect cardiovascular function within the last 6 months:
 - Heart rate < 55 bpm at screening
 - Cardiac conduction disorders such as incomplete left bundle branch block or second degree AV block Mobitz type I (Mobitz I) (either history or observed at screening)
 - Minor ECG findings at screening PR interval: >200 msec; QRS duration ≥120 msec; QTcF >430 msec (males); QTcF >450 msec (females)
 - History of or current significant cardiac disease including cardiac failure (NYHA functional class II-IV), myocarditis, cardiomyopathy, angina pectoris or myocardial infarction (within 6 months), unstable angina (within 6 months), stroke (within 6 months), TIA (within 6 months), decompensated heart failure requiring hospitalization (within 6 months) or uncontrolled arterial hypertension
 - History of (within the 6 months) or current cardiac disease such as heart failure NYHA class I, history of myocardial infarction prior to enrollment.
 - Patients receiving treatment with beta-blockers for cardiac disease/comorbidities
 - Any other condition which, in the opinion of the investigator, has a potential for AV conduction suppression and/or other risk factors that may require expanded cardiac monitoring
 - Patients diagnosed with right bundle branch block, either at the Screening visit for entry of the study or during the conduct of the study
- 15. Any of the following pulmonary conditions:
 - History of or active severe respiratory disease, including COPD, or pulmonary fibrosis,
 - Tuberculosis, except for history of successfully treated tuberculosis or a history of prophylactic treatment after positive PPD skin reaction

- Patient with severe asthma or asthma requiring regular treatment with oral steroids
- 16. Patients with any of the following hepatic conditions prior to screening:
 - history of alcohol abuse, chronic liver or biliary disease
 - total or conjugated bilirubin greater than 1.5 times ULN range, unless in the context of Gilbert's syndrome
 - alkaline phosphatase (AP) greater than 1.5 times the ULN range
 - AST (SCOT), ALT (SGPT) or Gamma-glutamyl-transferase (GGT) greater than 3 times the ULN range within the last 6 months
- 17. Any of the following abnormal laboratory values prior to screening:
 - Serum creatinine > 1.7 mg/dL (150 umol/L)
 - White blood cells (WBC) count <3,500/mm3 (<3.5 x 10(9)/L), while on oral DMT's at screening, except fingolimod
 - Lymphocyte count <500/mm3 (<0.5 x 10(9)/L) while on all DMT's at screening except fingolimod
 - Serum potassium > ULN
 - Or other clinically significant laboratory assessment (i.e. hypomagnesemia or hypokalemia)
 - For patients previously exposed to natalizumab, anti-JCV antibody positive and index > 1.5
- 18. Patients with the following neurological/psychiatric disorders prior to screening:
 - History of substance abuse (drug or alcohol) or any other factor (i.e. serious psychiatric condition) that may interfere with the patient's ability to cooperate and comply with the study protocol
 - Progressive neurological disorder, other than MS, which may affect participation in the study or require the use of medications not allowed by the protocol
- 19. Use of other investigational drugs at the time of enrollment or within prior 30 days; or five elimination half-lives, or until the expected pharmacodynamics effect has returned to baseline, whichever is longer.
- 20. History of hypersensitivity to the study drug or to drugs of similar chemical classes.
- 21. Homozygosity for CYP2C9*3/*3 or heterozygous for CYP2C9*2/*3 or CYP2C9*1/*3 (to be tested at screening) or refusal to test for CYP2C9 variants.
- 22. Concomitant use of MAYZENT and drugs that cause moderate CYP2C9 and moderate or strong CYP3A4 inhibition (Appendix 4).
- 23. Concomitant use of MAYZENT and drugs that cause moderate CYP2C9 and strong CYP3A4 induction (Appendix 4).
- 24. Use of cannabinoid or cannabidiol products 30 days prior to screening.
- 25. Any other disease or condition, which could interfere with participation in the study according to the study protocol, or with the ability of the patients to cooperate and comply with the study procedures.

Note 1: If a patient fails on one or more laboratory (or other) assessment criteria, as part of the screening process, the assessment (s) may be repeated at the discretion of the investigator and the patient may be included if criteria are then met, provided the assessments are completed within the screening period.

Note 2: In certain cases rescreening of patients that were previously determined ineligible may be permitted. When a patient is re-screened, a new patient identification number will be assigned and all screening assessments must be repeated. Each patient may be rescreened no more than 1 time.

No additional exclusions may be applied by the investigator, in order to ensure that the study population will be representative of all eligible patients.

6 Treatment

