Visit Name	Screening Visit	V1	V2 ¹²	V3	V4	Exit/V5		UPV
Visit Number	1	110	120	130	140	1999		UPV
Days	-28 days	1 (+3 days)	7 (±1 day)	28 (±5 days)	84 (±5 days)	168 (±5 days)	30- Day Telephone (±7 days)	
Obtain informed consent	Х							
MS History	Х							
Demography	Х							
Inclusion/Exclusion criteria	Х	Х						
Relevant Medical History	Х							
Physical Exam	S	S		S	S	S		S
Neurological Exam ⁸	X	X			X	X		X
Height	X					X		

Page 57 Protocol No. CBAF312AUS02

Period	Scree	ening				End of Treatment/St udy	Follow-up	Unplanned
Visit	Screening	Baseline ¹	Titration Treatment Period			End of Treatment/St udy	Safety	Unscheduled Visit
Visit Name	Screening Visit	V1	V2 ¹²	V2 ¹² V3 V4		Exit/V5		UPV
Visit Number	1	110	120	130	140	1999		UPV
Days	-28 days	1 (+3 days)	7 (±1 day)	28 (±5 days)	84 (±5 days)	168 (±5 days)	30- Day Telephone (±7 days)	
Weight	X	X			X	X		
Body Temperature	X	X		Χ	X	X		X
Respiration Rate	X	X		X	X	X		X
Blood Pressure	X	X		Χ	X	X		X
Heart Rate	X	X ²		Χ	X	X		X
Heart Rate 6 hours post Day 1 dose ²		Х						
Optical Coherence Tomography (OCT) ⁶		X _e			Х			
CYP2C9 Haplotype	Х							
Blood Chemistry/ Hematology	Х	Х		Х	Х	Х		Х
Coagulation and Thyroid	Х	Х		Х	Х	Х		Х
Hepatitis markers	Х							
CD19+ B-cell titer ¹⁰	X							

Period	Scree	ening			End of Treatment/St udy	Follow-up	Unplanned	
Visit	Screening	Baseline ¹	·		End of Treatment/St udy	Safety	Unscheduled Visit	
Visit Name	Screening Visit	V1	V2 ¹²	V3	V4	Exit/V5		UPV
Visit Number	1	110	120	130	140	1999		UPV
Days	-28 days	1 (+3 days)	7 (±1 day)	28 (±5 days)	84 (±5 days)	168 (±5 days)	30- Day Telephone (±7 days)	
VZV IgG Testing	X							
ECG (12 Lead)	X	X ⁷						
Pregnancy Test serum	S	S				S		
Pregnancy Test Urine				S	S			
AE/ SAE Assessment	Х	X		Х	Χ	X	Χ	X
Prior/Concomitant Medications	Х	Х		Х	Х	Х	X ⁵	Х
EDSS	Х							
TSQM-9		X		X	Χ	X		
C-SSRS		X				X		
Optional Trial Feedback Questionnaire ⁴		S			S	O		
Dispensation of medication ¹¹		S		S	S			

Period	Screening				Treatment		End of Treatment/St udy	Follow-up	Unplanned
Visit	Screening	Baseline ¹				End of Treatment/St udy	Safety	Unscheduled Visit	
Visit Name	Screening Visit	V1	V2 ¹²	V3	V4	Exit/V5		UPV	
Visit Number	1	110	120	130	140	1999		UPV	
Days	-28 days	1 (+3 days)	7 (±1 day)	28 (±5 days)	84 (±5 days)	168 (±5 days)	30- Day Telephone (±7 days)		
Drug accountability		S		S	S	S			
Dosage Administration Record		Х		Х	Х	X			
Washout ³		S							
IRT Call	S	S		S	S	S			

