Vital signs will be assessed at every visit. This will include blood pressure and heart rate measurements. BP will be medium sized cuff and the noon-dominant arm in the sitting position after 5 minutes of rest. Every effort should be made to use the same arm for the patient for all vital signs assessments and where possible, the same person doing the assessment. Clinically notable vital signs are defined in Appendix 1.

8.4.1 **Laboratory evaluations**

Table 8-4 **Laboratory Assessments**

I able 0-4	Laboratory Assessments	
Test Category	Test Name	
Hematology	Red blood cells, total White blood cells, Differential White blood cells (Basophils, Eosinophils, Lymphocytes, Monocytes, Neutrophils, platelet count, hemoglobin, hematocrit, mean corpuscular volume, mean corpuscular hemoglobin, mean corpuscular hemoglobin concentration and red blood cell morphology	
Chemistry	Alkaline phosphatase, ALT, AST, Gamma-glutamyl-transferase (GGT), Bicarbonate, Calcium, Magnesium, Phosphorus, Chloride, Sodium, Potassium, Creatinine, Creatine kinase, Direct Bilirubin, Indirect Bilirubin, Total Bilirubin, Total Cholesterol, LDL, HDL, Total Protein, Triglycerides,	
	Glucose, amylase	
Coagulation	Prothrombin time (PT) , Partial thromboplastin time (PTT)	
Thyroid	T3 (free), T4 (free), TSH	
Hepatitis markers	HBV-DNA, HbsAg, HbsAb, HbcAb, HCV RNA-PCR (baseline)	
Additional tests	Serology: anti-hepatitis A virus IgM, hepatitis B surface antigen and anti-hepatitis B core antigen IgM, anti-hepatitis C virus IgG or IgM, anti-hepatitis E virus IgM (positive IgM and/or IgM: do HEV-RNA PCR; if negative, patient can be included), Anti-VZV IgG, CYP2C9 haplotype testing	

Test Category	Test Name
	CD19+ Titers
Pregnancy Test	Serum / Urine pregnancy test

Clinical Chemistry

Blood samples will be collected at the scheduled visits indicated in Table 8-1, and the parameters assessed will include: electrolytes (Na, K, Cl, bicarbonate, Ca, Mg, P), random glucose, albumin, alkaline phosphatase, creatinine, ALT, AST, GGT, amylase, total bilirubin, conjugated bilirubin, total cholesterol, CRP, triglycerides, HDL and LDL.

Hematology

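### The Note to exclusion criterion 9 lets a hepatitis E PCR settle suspected false-positive hepatitis A, B or C serology, and no eligibility rule uses the HBV-DNA and HCV-RNA tests already scheduled

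*Protocol*

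**What the plan says.** Protocol section 5.2, exclusion criterion 9, excludes patients whose screening serology indicates acute or chronic hepatitis A, B, C or E. For hepatitis E it includes a sensible confirmatory step: after positive serology, "perform HEV-RNA PCR and if negative, patient can be included".

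The Note beneath the criterion then sets a general exception. The trigger is broad: "If the treating physician suspects false positive hepatitis serology results". The example given is an antibody pattern of acute infection without matching enzyme elevation or clinical signs. In that situation "HEV-RNA PCR will be performed and will be the deciding factor to determine whether the patient has hepatitis A, B, C, or E". After a negative result the physician may record, in source data and an eCRF comment, "that the serology results are considered false positive and consider including the patient". The same rule stands in the protocol summary and in section 8.4.1 under Serology.

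Two other nucleic acid tests are planned. The hepatitis row of Table 8-4 reads "HBV-DNA, HbsAg, HbsAb, HbcAb, HCV RNA-PCR (baseline" (closing bracket omitted here), and Table 8-1 marks the row "Hepatitis markers" at Screening.

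**The concern.** An HEV-RNA PCR detects hepatitis E virus. A negative result says nothing about hepatitis A, B or C, yet the Note makes it decisive for all four. A physician who follows the text literally could call a true hepatitis B or C result a false positive on the strength of an irrelevant test. That patient would then start a drug that Appendix 3 of the protocol describes as potentially immunosuppressive. The tests that do bear on hepatitis B and C are on the laboratory list, but the rule does not point to them.

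What is at stake is the safety of individual patients at entry. On-study chemistry (Days 28, 84 and 168) and the liver stopping rules of Appendix 2 limit harm afterwards, but they do not prevent enrolment.

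**Working it through.** No calculation applies, because the point concerns an eligibility rule. The check is to set every relevant provision side by side.

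| Virus | Serology that excludes | Nucleic acid test named in the protocol | Is that test used in an eligibility rule? | Test the Note makes decisive |
|---|---|---|---|---|
| A | anti-HAV IgM (5.2, 8.4.1) | none | not applicable | HEV-RNA PCR |
| B | HBsAg, anti-HBc IgM (5.2, 8.4.1) | HBV-DNA (Table 8-4) | no | HEV-RNA PCR |
| C | anti-HCV IgG or IgM (8.4.1 only) | HCV RNA-PCR (Table 8-4) | no | HEV-RNA PCR |
| E | anti-HEV IgM (5.2, 8.4.1) | HEV-RNA PCR (5.2, 8.4.1) | yes | HEV-RNA PCR |

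1. The Note names 4 viruses and its deciding test informs on 1, so it is uninformative for 4 − 1 = 3.
2. The protocol names 3 nucleic acid tests. Only the HEV-RNA PCR has an eligibility rule, so 3 − 1 = 2 have none.
3. The Note appears in 3 places (summary, 5.2, 8.4.1) with the same rule each time, so no copy corrects another.
4. SAP Table 5, code EXCL09, repeats the serological criterion and adds no rule on nucleic acid results.
5. On timing, Table 8-4 labels the hepatitis row as baseline while Table 8-1 places it at Screening. Either way sampling comes before dosing, since footnote 1 of Table 8-1 puts baseline assessments ahead of the first dose. No text requires the HBV-DNA or HCV-RNA result to be reviewed before the Note is used.
6. The criterion 9 bullets in 5.2 and in the summary contain no hepatitis C marker, although the criterion covers hepatitis C and 8.4.1 makes positive anti-HCV exclusionary.

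The hepatitis E bullet uses the HEV-RNA PCR correctly. The likeliest explanation is that its wording was carried into a Note covering all four viruses.

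**The case against.** The strongest reply is that the Note compels nothing. A patient who reaches it already has positive serology and is excluded under criterion 9 (for anti-HCV, under 8.4.1). The physician must first suspect a false positive, and after a negative PCR is only permitted to document that and consider inclusion. Declining leaves the patient excluded. This is correct and limits the point considerably.

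It also disposes of a stronger reading. Section 5.2 states "No additional exclusions may be applied by the investigator in order to ensure that the study population will be representative of all eligible patients", and a reader might infer that an investigator holding a positive HBV-DNA or HCV-RNA result is barred from acting on it. The documents do not support that. Refusing an optional exception to a listed criterion is not an additional exclusion.

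Other criteria give further grounds. Criterion 8 covers "Patients with active systemic bacterial, viral, or fungal infections". Criterion 17 covers other clinically significant laboratory findings; its examples are electrolytes, but a positive viral nucleic acid result can reasonably be read into it. Criterion 16 covers chronic liver disease and raised liver tests, though its enzyme limits help little in the Note's own example, where enzymes are not raised. Criteria 13 and 25 leave room for judgement. Since the relevant tests are scheduled at Screening, the physician should have the results. For harm to follow, the physician would have to hold or overlook a positive result, still suspect false-positive serology, apply none of these criteria and choose to enrol.

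The Note's example is also narrow: an acute antibody pattern, whereas HBsAg is an antigen. It is offered only as an example, so it does not limit the trigger.

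These points reduce the risk. None makes the sentence correct, because no criterion mentions HBV-DNA or HCV-RNA and the one specific instruction names the wrong test for three viruses.

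**Conclusion.** The Note is wrong as written. It is a minor patient-safety wording error, probably a drafting slip. It can produce a wrong eligibility decision for hepatitis A, B or C, but only if a physician chooses to use the exception and no other criterion is applied. Few patients are likely to be affected; that is a judgement, since the documents give no rate of positive or disputed serology.

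A reader might infer that enrolling such patients would distort the primary result. Nothing in the documents supports this. The primary endpoint remains the proportion of Safety Set patients with a drug-related adverse event, and its definition, analysis set and planned precision do not depend on the Note. Under SAP Tables 5 and 7, even a recorded breach of criterion 9 is reported with the patient kept in all analyses.

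The conclusion rests on one premise from outside the text, that an HEV-RNA PCR informs only on hepatitis E. The hepatitis E bullet of criterion 9 uses it in just that way.

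**What to change.** Change all three copies of the Note (summary, 5.2, 8.4.1):

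- Limit the HEV-RNA PCR to hepatitis E serology.
- For hepatitis B or C serology, allow a false-positive determination only if the HBV-DNA or HCV RNA-PCR result already listed in Table 8-4 is negative and has been reviewed before the first dose.
- For anti-HAV IgM, rely on repeat testing under Note 1 of section 5.2.

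For consistency, add the anti-HCV marker from 8.4.1 to the criterion 9 bullets in 5.2 and the summary. A longer confirmatory algorithm, such as also demanding a non-reactive repeat HBsAg, is not needed here: it has no source in the documents, and Note 1 already allows repeat testing.

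The cost is a wording amendment or clarification letter. The nucleic acid tests are already scheduled. The downside is possibly a few more screen failures and a short wait within the screening period of about 28 days. Past uses of the exception should be traceable, since the Note provides for source and eCRF documentation.

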6.1 Study treatment

6.1.1 Investigational and control drugs

Chemical Name: Siponimod

Other Names: BAF312, Mayzent ®

Classification: Oral sphingosine 1-phosphate receptor modulator

The investigational drug siponimod will be provided as film coated tablets. Please refer to the pharmacy manual provided for specific instructions.

The study medication will be administered orally, once daily, with or without food.

Should titrated patient miss one day of titration or more, the patient will need to restart the titration with Day 1 dosing (0.25mg), including Day 1 cardiac assessments (pre-dose ECG and 6-hour post dose heart rate). It is strongly recommended, during the titration phase, that a member of the study staff contact the patient, once daily via phone, to remind them to take their study medication as required. This is because restarting the titration will require the patient to come in for an unscheduled visit to do a pre-dose ECG assessment and 6 hour post-dose heart rate (holter telemetry monitoring).

Furthermore, if maintenance treatment (2mg) is interrupted for 4 or more consecutive daily doses, treatment must be re-initiated with the 5-day titration, including pre-dose ECG and 6-hour post-dose heart rate (holter telemetry monitoring) at an unscheduled visit. Treatment interruptions for up to 3 missed consecutive daily doses does not require re-titration, and treatment should be continued at the maintenance dose level.

If the patient has missed greater than 30 consecutive days of treatment, using his/her best medical judgement, the PI should consider terminating the patient from the study.

Treatment arm	# of patient's	Type of study drug	Compound	Min. Dose	Max. Dose	Frequency	Formulation	Admin Route	Generic acceptabl e
Arm 1	300 - 400	Investigational	Siponimod	0.25 mg	2 mg	Daily	Tablet	Oral	No

